11.2.12 Change in NEWS2 from baseline

Changes in NEWS2 score will be reported at days 3, 5, 8, 11, 15, and 29.

11.2.15 Change in IL-8 and downstream cytokines.

Circulating IL-8 and additional cytokines (IL1B, IL2, IL4, IL5, IL6, IL7, IL9, IL10, IFNgamma, TNFalpha and others) will be measured at baseline and at additional time points when possible (day 8, 15, 22, 29).

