2.1 Exploratory Objectives

- To assess the **change in LDH, D-Dimer, CRP, ESR, NLR and absolute lymphocytes** before and after treatment and over time (every 2 days for duration of hospitalization).
 - To assess the **change in sIL-6** before and after treatment and over time.
 - To evaluate **radiological response** by comparing % of lung fields with infiltrates on chest imaging (CXR and CT) through independent radiology review.
 - To measure **time on ventilation** measured from time of intubation to time of definitive extubation
 - To measure time to improvement in **NEWS2 score to ≤ 2**
 - To evaluate the **change in NEWS2** from baseline.
 - To measure proportion of patients with **multi-organ failure at 1 month**.
 - To assess whether **IL-8 and other key cytokines (TNF, IL-1b, IL-6) at baseline and during treatment are predictive of treatment efficacy** by quantification of circulating IL-1b, IL8, TNFalpha and IL-6 levels over time.
 - To quantify **changes in humoral immune responses** by antibody profiling at baseline and following treatment.
 - To **characterize PK** of BMS-986253 in cancer patients with severe COVID-19.

[figure not shown]

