10. STUDY CALENDAR

Every effort should be made to keep visits, tests, and procedures on schedule. Acceptable deviations are listed below.

	Screening Evaluation ^a	During Hospitalization (daily unless indicated)	Day 29 and Follow-up (after discharge) ^f
Informed consent	X		
Medical history (including baseline ECOG)	X		X
Review of medications	X	X	X
Physical assessment ^k	X	X	
Vital signs (including SpO ₂ /FIO ₂ if on supplemental oxygen)	X	(3 times per day) ⁱ	
Height and weight	X		
Laboratory studies ^b	X	X	
Inflammatory markers ^j	X	Every 2 days	
NLR and absolute lymphocyte count	X	X	
Serum ^c	X	Every 7 days (+/- 2 days) ^c	
NEWS2 score ^d	X	X	
7-point ordinal scale ^l	X	X	
Chest imaging (optional) ^e	X	Every 7 days (+/- 2 days) ^e	
BMS-986253 dose		Every 2 weeks for 1-3 doses ^g	
Toxicity assessment		X	X ^h

a: The screening (pre-treatment) evaluation should be conducted within 1 day prior to dose of BMS-986253. If screening done on same day as treatment then treatment day 1 assessments do not need to be repeat (screening assessments will suffice)
b: Laboratories should include hemoglobin, hematocrit, white blood cell count with differential (including absolute eosinophil count), platelets, sodium, potassium, chloride, bicarbonate, urea nitrogen, creatinine, glucose, calcium, albumin, total protein, bilirubin, alanine aminotransferase (ALT), aspartate aminotransferase (AST), alkaline phosphatase. Prothrombin time (PT/INR), activated partial thromboplastin time (APTT) will be drawn at baseline and then as clinically indicated.
c: Serum samples should be collected for cytokine and PK analysis at screening, day 8, 15, 22, 29, and EOT if possible (not required). Should be collected prior to the treatment dose of day 15 and 29. For patients ready for discharge prior to day 8, a serum sample should be collected, when feasible, prior to discharge.
d: NEWS2 score is calculated considering respiratory rate, oxygen saturation, systolic blood pressure, pulse rate, level of consciousness/confusion, temperature.
e: CT chest or CXR at baseline (within 2 days of enrollment) and after 7 days (+/- 2 days) if clinically indicated.
f: Can be done by phone: at day 29 (+/- 1 day) and every 1 month (+/- 1 week) (until 100 days following last dose of treatment), then every 3 months (+/- 1 month) from registration to up to 1 year follow up.

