10.1 Screening/Pretreatment Evaluation

Before initiating any screening activities, the scope of the study should be explained to each patient. Patients should be advised of any known risks inherent in the planned procedures, any alternative treatment options, their right to withdraw from the study at any time and for any reason, and their right to privacy. After this explanation, patients should be asked to sign and date an IRB-approved informed consent form that meets the requirements of the Code of Federal Regulations (Federal Register Vol. 46, No. 17, January 27, 1981, part 50).

The pretreatment/screening visit will determine patient eligibility according to the inclusion and exclusion criteria. All subjects must undergo a number of baseline evaluations as part of this screening visit, as detailed below. All of these evaluations should be conducted within 1 day of starting the protocol. This information is also summarized in the Study Calendar (Table 1).

- informed consent
- demographic information
- medical history, including review of systems and baseline ECOG score.
- physical assessment
- vital signs: temperature, pulse, blood pressure, respiratory rate, oxygen saturation and FIO₂ and SpO₂/FIO₂
- height and weight
- current medication list, including drug allergies/adverse events
- hematological laboratories (hemoglobin, hematocrit, white blood cell count with differential [including absolute eosinophil count], platelets)
- coagulation profile (INR, aPTT)
- serum chemistry (sodium, potassium, chloride, bicarbonate, urea, creatinine, glucose, calcium, albumin, protein, bilirubin, ALT, AST, alkaline phosphatase)
- CRP, D-Dimer, LDH, sIL-6 level
- Neutrophil-to-lymphocyte ratio (NLR), absolute lymphocyte count
- NEWS2 score
- 7-point ordinal score
- CT or CXR of the chest (optional)
- Sera for biomarker and PK analysis.

After all relevant screening information is documented, registration should be finalized and appropriate documents (*i.e.*, signed informed consent, supporting source documentation for eligibility) should be faxed or emailed to CPDM Central Registration Office for review.

Information on patients who do not meet eligibility criteria to participate in this study (*i.e.*, screening failures) should also be captured.

10.2 During Hospitalization:

The following must be performed during hospitalization (if screening assessments done <1 day prior to first treatment dose, they do not need to be repeated on Day 1 of treatment).

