- review of medication list daily
- review of toxicity/adverse events daily
- vital signs (pre- and post-infusion of BMS-986253) and three times per day including temperature, heart rate, blood pressure, respiratory rate, oxygen saturation and FIO₂ and SpO₂/FIO₂ if on supplementation oxygen.
- physical exam daily
- hematological laboratories (hemoglobin, hematocrit, white blood cell count with differential [including absolute eosinophil count], platelets) daily
- coagulation profile (INR, aPTT) as clinically indicated.
- serum chemistry profile (sodium, potassium, chloride, bicarbonate, urea, creatinine, glucose, calcium, albumin, total protein, bilirubin, ALT, AST, alkaline phosphatase) daily
- CRP, D-Dimer, LDH, sIL-6 level every other day
- Neutrophil-to-lymphocyte ratio (NLR), absolute lymphocyte count daily
- NEWS2 score daily
- 7-point ordinal score daily
- CT or CXR of the chest weekly (+/- 2 days) (optional)
- Sera for biomarker and PK analysis day 8, 15, 22, 29, and EOT (+/- 2 days). Where possible, the Day 15 and 29 PK samples should be collected just prior to dosing (optional). For patients ready for discharge prior to day 8, a serum sample should be collected, when feasible, prior to discharge.
- Patients randomized to anti-IL-8 therapy will receive BMS-986253 every 2 weeks (+/- 2 days) x 1-3 doses, with 2nd dose given if patient still hospitalized and then 3rd dose optional if patient still hospitalized with severe COVID-19. Patients randomized to control will receive standard of care.

10.3 Follow-Up After Discharge:

Following completion of therapy, patient will have follow up by phone every 30 days for the first 100 days following the last dose of therapy. Patients will then have follow up by phone every 90 days (+/- 30 days) for up to 1 year. In addition, patients will be assessed 28 days (+/- 2 days) following start of treatment whether they are discharged or in the hospital. These assessments will include:

- review of medication list
- review of toxicity/adverse events (for up to 100 days following last dose of treatment)
- Evaluation of Katz basic ADLs and Lawton IADLs (Appendix C and D)

- assessment for survival

Patients withdrawing from the study early because of adverse events should be followed until the adverse event has either resolved or stabilized. Reasons for premature withdrawal should be determined and documented.

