11.2 Secondary Endpoints

11.2.1 *Time to death*

The time to death will be defined as the time from onset from symptoms until death from any cause. Patients who are alive or lost to follow-up at the cut-off date will be censored from this analysis.

11.2.2 *Mortality at 1 month*

1-month mortality is defined as the percentage of patients who have died 1 month from the time of start of treatment.

11.2.3 *Time to intubation*

The time to intubation will be defined as the time from symptom onset until time of intubation. Any patients already intubated at enrollment will be censored from this analysis.

11.2.4 *Time to improvement in oxygenation*

The time to improvement in gas exchange will be defined as the time from time of start of treatment until a $\geq 30\%$ decrease in oxygen requirement compared to

baseline [or elimination of oxygen requirement] without a decrease in SpO2 sustained for at least 48hrs or until discharge.

11.2.4 *Proportion of patients requiring ICU admission at 1 month.*

The proportion of patients requiring ICU admission will be calculated as the number of patients requiring ICU admission over the course of their hospitalization over the number of evaluable patients.

11.2.5 *Safety and Toxicity*

All subjects receiving at least one dose of the study drug will be evaluated for safety by monitoring symptoms, physical examinations, and laboratory tests. Adverse events will be classified and graded according to the NCI Common Toxicity Criteria version 5.0 (see Appendix A). The absolute number and frequency of each adverse event will be reported, and subdivided according to toxicity grade. A description of adverse events by treatment arm will also be reported. A particular adverse event occurring more than once in the same subject will be counted only once and at its worse grade.

11.2.6 *Duration of Hospitalization*

Duration of hospital admission will be measured from the time of admission until the time of discharge.

11.2.7 *7-point Ordinal Scale Score*

The mean/medians of the 7-point ordinal raw scores at day 14 from the start of treatment will be computed and compared between the treatment and control groups.

Exploratory Endpoints.

11.2.8 *Change in inflammatory markers from baseline*

Changes in LDH, D-Dimer, CRP, ESR, NLR and absolute lymphocytes before and after treatment and over time will be measured every other day during hospitalization.

11.2.9 *Change in circulating sIL-6 levels from baseline*

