13.2 Study Endpoints and Analysis Plan

All subjects who receive at least one dose of study drug will be considered evaluable and included in the efficacy and safety analysis.

Analytic plan for primary objective:

The primary efficacy null hypothesis of the equality of time to improvement (2 points) in clinical status curves will be tested with the log-rank test. The overall type I error for the primary analysis will be considered one-sided alpha of 0.025. Kaplan-Meier estimates will be reported for each of the two arms with median time to improvement and 95% confidence intervals (CI). Cox regression will be employed to estimate the treatment effect (HR) and 95% CI.

Analytic plan for secondary and exploratory objective:

We will estimate the distributions of all time-to-event endpoints using the Kaplan-Meier method and if possible, provide medians (95% CI). Comparisons between survival curves will be assessed using log-rank tests and Cox regression models.

For each arm, we will estimate the 1-month mortality rate and incidence of adverse events graded by CTCAE v5.0 using the exact 95% confidence intervals. Comparisons between the two arms will be assessed using chi-squared or Fisher's exact tests. The mean/medians of the 7-point ordinal scores at day 14 after the start of treatment will be computed and compared between the two groups using two-sample t-test or the equivalent non-parametric Wilcoxon Rank-Sum test if normality is not satisfied.

Changes in exploratory endpoints (before and after treatment) will be quantified using means (95% CI) and/or medians (inter-quartile ranges) for non-normal data. Comparisons between the two arms will be made using two-sample independent t-tests or the non-parametric equivalent, Wilcoxon Rank-Sum test. The associations between baseline levels and/or changes over time of IL-8 and other key cytokines (TNF, IL-1b, IL-6) with outcomes will be assessed using regression models.

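### NEWS2 and inflammatory markers are measured only in hospital, but the plan has no rule for how discharged or dead patients enter the between-arm comparisons of change

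*Combined protocol and SAP*

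**What the plan says.** **Objective.** Section 2.1 lists as exploratory: "To evaluate the change in NEWS2 from baseline". It also lists change in LDH, D-dimer, CRP, ESR, NLR, lymphocytes and sIL-6, before and after treatment and over time.

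**Collection.** Section 10.2 opens with "The following must be performed during hospitalization" and includes "NEWS2 score daily". For the markers, Section 11.2.8 says "NLR and absolute lymphocytes before and after treatment and over time will be measured every other day during hospitalization", and Section 11.2.9 has the same schedule for sIL-6. In the Study Calendar, the column for day 29 and follow-up is blank for NEWS2, vital signs, laboratory studies and inflammatory markers. Footnote f says of those contacts: "Can be done by phone: at day 29 (+/- 1 day". The list in Section 10.3 covers medications, toxicity, activities of daily living and survival only.

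**Reporting and testing.** The section titled Change in NEWS2 from baseline says "Changes in NEWS2 score will be reported at days 3, 5, 8, 11, 15, and 29". For changes in exploratory endpoints, Section 13.2 says "Comparisons between the two arms will be made using two-sample independent t-tests or the non-parametric equivalent, Wilcoxon Rank-Sum test". No section states what value or rank a discharged or dead patient receives, or that such patients are left out.

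**The concern.** A patient who goes home or dies has no NEWS2 or marker value from that day on. If the tests in Section 13.2 are run on whatever values exist, each later day compares only patients still in hospital. Discharge is close to the effect that the trial hopes to produce. On the 7-point scale, a patient who enters at 4 (supplemental oxygen) reaches the two-point improvement only at 6 or 7, that is, shortly before or at discharge. Treatment may therefore change who remains, and the remaining groups are no longer the randomised groups.

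At stake is the reading of supporting evidence. A diluted or reversed NEWS2 or CRP difference could be taken as evidence about the drug when it partly reflects who was still there to be measured.

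**Working it through.** The plan states no figure for these comparisons, so there is none to reproduce. It also gives no discharge rates, NEWS2 variances or slopes. Everything below shows what can happen under assumptions. Differences are drug minus control in NEWS2 change; negative favours the drug.

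**1. How many patients might remain.** Inputs: 92 and 46 patients (Section 13.1), and the synopsis medians of 5 days (control) and 2 days (anti-IL-8), used as a stand-in for time to leaving hospital. Section 13.1 gives these medians in the opposite direction and the two places need reconciling; the synopsis direction is an assumption here. The stand-in is rough, since a two-point gain need not mean discharge, so a version with stays three times longer is also shown. Formula: number remaining = n × 0.5^(day/median).

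| Day | Control, median 5 | Drug, median 2 | Control, median 15 | Drug, median 6 |
|---|---|---|---|---|
| 8 | 46 × 0.330 = 15 | 92 × 0.0625 = 6 | 46 × 0.691 = 32 | 92 × 0.397 = 37 |
| 15 | 46 × 0.125 = 6 | 92 × 0.0055 = 0.5 | 46 × 0.500 = 23 | 92 × 0.177 = 16 |
| 29 | 46 × 0.018 = 0.8 | about 0 | 46 × 0.262 = 12 | 92 × 0.035 = 3 |

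**2. Two-group calculation.** A share w of patients is responsive. Their median stay is 5s days on control and 2s on drug, with s = 1, 2 or 3. The others have a median stay of 20 days in both arms. Change is -3 for responsive patients in hospital, 0 for the others in hospital, and -5 once home. There are no deaths. With a = w × 0.5^(day/m) and b = (1 - w) × 0.5^(day/20):

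- in-hospital mean = -3a/(a + b)
- all-randomised mean = -3a - 5(1 - a - b)

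Day 8, w = 0.5, s = 2:

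- Drug (m = 4): a = 0.125, b = 0.379. In hospital -0.375/0.504 = -0.74; all -0.375 - 5 × 0.496 = -2.86.
- Control (m = 10): a = 0.287, b = 0.379. In hospital -0.862/0.666 = -1.29; all -0.862 - 5 × 0.334 = -2.53.
- Difference: +0.55 in hospital, -0.32 over all randomised.

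For w = 0.5 and 0.7 with s = 1 to 3, the day-8 difference is +0.39 to +1.03 in hospital, against -0.27 to -0.45 over all randomised. At day 3 it is already +0.14 to +0.46 against -0.16 to -0.43, because this model lets patients leave at a constant rate from the start.

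**3. Simulated NEWS2 paths, benefit in 60% of patients.** Baseline mean 7, SD 1.5 (limited to 4-12); daily noise SD 1. Natural improvement is 0.45 points/day in the responsive 60% and 0.05 in the rest (SD 0.15 each). The drug adds 0.3 points/day in the responsive group only. Patients go home when the score is 2 or less after 3 or less the day before. No deaths; 800 trials.

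| Day | In hospital, drug / control | All randomised | In hospital only |
|---|---|---|---|
| 3 | 91.6 / 45.9 | -0.54 | -0.54 |
| 5 | 86.9 / 45.3 | -0.89 | -0.82 |
| 8 | 64.5 / 41.4 | -1.21 | -0.53 |
| 11 | 44.2 / 34.3 | -1.12 | +0.64 |
| 15 | 35.5 / 25.5 | -0.73 | +1.15 |
| 29 | 27.6 / 15.1 | -0.17 | +0.30 |

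**4. Simulated paths, same benefit in everyone (0.15 points/day).** At day 15 the difference is -1.29 over all randomised and -0.90 in hospital. With deaths also leaving the set, it is -1.34 and -0.66. The effect shrinks but keeps its sign on average.

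**The case against.** Several counter-arguments have weight.

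- **The plan does not say that arms are tested at each day.** The NEWS2 section says that changes are reported at six days, and Section 13.2 names no days. This stands for the markers: the text says only that they "will be measured every other day during hospitalization", so a by-day comparison is a fair reading of the over-time objective, not a stated rule. For NEWS2 the six days and the test in Section 13.2 together make it the natural reading. The missing rule for discharge and death is a fact either way.
- **A reader might infer that every comparison is confined to the sicker patients, or that a working drug will look harmful.** The documents do not support this. Deaths also leave the set, so those left are not simply the sickest. In the path model day 3 is untouched. A uniform benefit is diluted, not reversed. Reversal needs the benefit to be concentrated in patients who then go home, and nothing in the documents says that it is.
- **Other endpoints keep these patients.** The day-14 ordinal score gives death a 1 and not hospitalised a 7, and time to NEWS2 of 2 or less can count recoveries. They limit the harm but do not repair the change-from-baseline comparisons.
- **The endpoints are exploratory.** True. No part of the primary type I error and no stopping decision rests on them.

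**Conclusion.** The gap is real: both kinds of measurement stop at discharge or death, NEWS2 change is scheduled for reporting to day 29, and the between-arm test has no rule for those who have left. From about day 8 under the path model (earlier if patients leave at a constant rate from the start), the NEWS2 comparison would rest on a subset selected after randomisation. On a fair reading, so would later marker comparisons.

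Size and direction are open. The assumed models give anything from moderate dilution to a reversal of about a point, and the documents contain no discharge rates to choose between them. The primary conclusion is unaffected. Minor; worth considering while the analysis text can still be changed.

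**What to change.** In the section titled Change in NEWS2 from baseline (cite it by title, since two sections carry the number 11.2.12) and in Section 13.2:

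1. At each listed day, make the between-arm NEWS2 comparison a Wilcoxon rank-sum test over all randomised patients as assigned. Rank death by that day worst, patients in hospital by NEWS2 change, and patients discharged alive best. Day 29 can stay, because discharged patients have a rank and those still in hospital have a daily score.
2. State the analysis set explicitly. Sections 13.2 and 13.5.1 both require at least one dose of study drug, which is narrower than all randomised patients.
3. Label in-hospital means or medians of NEWS2 and of the markers as descriptive. Give the number contributing per arm and day, and say that later-day marker tests are not to be read as randomised comparisons.

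Cost: a few lines of text and slightly more analysis, with no new visits, since discharge and survival are already collected. The NEWS2 result becomes a rank comparison instead of a mean in points, and at later days it overlaps with the day-14 ordinal comparison.

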11.2.16 Change in humoral immune response

The humoral immune response will be assessed by protein microarray antibody profiling at baseline and at additional time points when possible (day 8, 15, 22, 29).

11.2.17 To characterize PK of BMS-986253

Will assess PK at screening, day 8, 15, 22, 29, and EOT by collection of serum at these time points when feasible. For patients ready for discharge prior to day 8, a serum sample should be collected, when feasible, prior to discharge.

Stopping Rules

The study may be discontinued by the data and safety monitoring committee (DSMC), the Food and Drug Administration (FDA), or other regulatory authorities. Any unforeseen deaths or serious adverse events may, after a discussion between the principal investigator, prompt an interruption to study accrual pending a full investigation into the circumstances surrounding the event.

Continuous Toxicity Monitoring

As this trial will be the first time an anti-IL-8 will be tested in patients with severe COVID-19, safety will be monitored on a continual basis. Sequential boundaries will be used to monitor dose-limiting toxicity rate.¹⁶ The accrual will be halted if excessive numbers of dose-limiting toxicities are seen, that is, if the number of dose-limiting toxicities is equal to or exceeds b_n out of n patients with full follow-up (see Table 3). This is a Pocock-type stopping boundary that yields the probability of crossing the boundary at most 0.05 when the rate of dose-limiting toxicity is equal to the acceptable rate of 30%. For the purposes of this stopping rule, dose-limiting toxicities will be defined as any treated related grade 3 or 4 toxicity.

Table 3. Toxicity Monitoring

Number of Patients, n	1	2	3	4	5	6-7	8-9	10-11	12-14	15-16	17-18	19-21	22-23	24-25	26-28	29-30	31-33	34-36	37-38
Boundary, b_n^*	-	-	-	4	5	6	7	8	9	10	11	12	13	14	15	16	17	18	19
Number of Patients, n	39-42-	44-	47-	50-	52-	55-	58-	60-	63-	66-	67-	71-	74-	77-	79-	82-	85-	98-	
	41	43	46	49	51	54	57	59	62	65	67	70	73	76	78	81	84	87	90
Boundary, b_n^*	20	21	22	23	24	25	26	27	28	29	30	31	32	33	34	35	36	37	38
Number of Patients, n	91-																		
	92																		
Boundary, b_n^*	39																		

*This boundary is equivalent to testing the null hypothesis, after each patient, that the event rate is equal to 30%, using a one-sided level 0.009 test.

For example, based on the boundaries above, if 12 out of the first 20 patients enrolled in the anti-IL-8 arm experience dose-limiting toxicities, the trial will be stopped for safety. In this case, the 95% exact confidence interval will be (0.36, 0.81), with the lower confidence limit exceeding the event rate (30%).

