Duration of Treatment: Subjects randomized to receive BMS-986253 will receive treatment for up to 4 weeks while hospitalized or intolerable toxicity or side effects. Patients who are discharged prior to 2 weeks after the first treatment, will not receive additional doses of therapy. Patients still with severe respiratory symptoms and hospitalized at 4 weeks may receive an additional treatment dose. Subjects randomized to the control arm will receive standard of care therapy as determined by their treating physician.

PK assessments and Correlative Studies: Serum will be collected at baseline and then weekly during hospitalization if feasible. For patients ready for discharge prior to day 8, a serum sample should be collected, when feasible, prior to discharge.

Duration of Follow up: Toxicity and laboratory tests will be graded using the NCI CTCAE v5.0 scoring system. Adverse events will be assessed continuously from the inpatient medical record during the study and for **100 days** after the last dose of treatment. Laboratories as outlined in **Section 11** will be collected daily during hospitalization. Post-discharge medical history and survival will be assessed monthly until 100 days following the last dose of therapy and then every 3 months for up to 1 year.

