7. TREATMENT PLAN

7.1 Agent Administration

Treatment will be administered on an inpatient basis. Reported adverse events and potential risks for BMS-986253 are described in **Section 10**. Appropriate dose modifications for BMS-986253 are described in **section 9**. No investigational therapies other than those described below may be administered with the intent to treat the patient's COVID-19 while the patient is enrolled in the study.

REGIMENT DESCRIPTION					
Agent	Premedications; Precautions	Dose	Route	Schedule ⁺	Cycle Length
BMS-986253	No specific premedications or precautions	2400mg	IV over 120 minutes (+/- 10 minutes)*	Days 1, 15, 29	6 weeks

*Infusion time will be 180 minutes (+/- 10 minutes) for patients <35kg.

⁺ Day 15 dose will be given if still hospitalized; day 29 dose is optional and will be given if patient hospitalized with severe respiratory symptoms.

7.2 Management of Infusion Reactions:

Since BMS-986253 contains only human Ig protein sequences, it is unlikely to induce hypersensitivity reactions. In the CA027-001 study, an infusion reaction (Grade 1) was observed in 1 patient and in the CA027-002 study 2 patients experienced infusions reactions (1 patient with Grade 2; 1 patient with Grade 4). If such a reaction were to occur, it might manifest with fever, chills, rigors, headache, rash, pruritus, arthralgia, hypotension, hypertension, bronchospasm, or other allergic-like reactions. All serious infusion reactions should be reported to BMS. All Grade 3 or 4 infusion reactions should be reported within 24 hours (excluding holidays and weekends) to the CUMC Sponsor-Investigator and BMS Medical Monitor and reported as an SAE. Infusion reactions should be graded according to NCI CTCAE v5.0 guidelines.

Treatment recommendations for infusion reactions are provided below and may be modified based on local treatment standards and guidelines, as appropriate.

For Grade 1 symptoms (mild reaction; infusion interruption not indicated; intervention not indicated):

- Remain at bedside and monitor participant until recovery from symptoms. The following prophylactic pre-medications are recommended for future infusions: diphenhydramine 50 mg (or equivalent) and/or acetaminophen/paracetamol 325 mg to 1000 mg at least 30 minutes before study treatment administrations.

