7.8 Criteria for Removal from Study

Patients will be removed from study when any of the criteria listed in Section 8.6 applies. The reason for study removal and the date the patient was removed will be documented in the Case Report Form.

DOSING DELAYS/ DOSE MODIFICATIONS

7.9 **Criteria and Procedures for Dose Modifications and Interruptions**

Dose escalation/reduction is not permitted in this study in order to allow better evaluation of the safety and efficacy. However, if toxicities occur, subsequent doses of BMS-986253 should follow the below guidelines:

Toxicity	Grade	Hold Treatment (Y/N)	Timing of Treatment Restart	Dose Schedule for Treatment Restart	Discontinue Subject
	1, 2	No	N/A	N/A	N/A

Hematologic Toxicity	3, 4	Yes	Toxicity resolves to \leq Grade 1 or baseline	Restart at same dose. However, for all Grade 4 hematologic toxicities, treatment may not be restarted.	Toxicity does not resolve to \leq Grade 1 or baseline by the time of next treatment dose. Permanent discontinuation should be considered for any severe or life-threatening event.
Non-Hematologic Toxicity Note: Exception to be treated similar to Grade 1 toxicity: - Grade 2 fatigue - Grade 3 rash in patients who have not experienced a grade 3 drug-related skin AE	1	No	N/A	N/A	N/A
	2	Consider holding for persistent symptoms	Toxicity resolves to \leq Grade 1 or baseline	Restart at same dose	Toxicity does not resolve to \leq Grade 1 or baseline by the time of next treatment dose. Permanent discontinuation should be considered for any severe or life-threatening event
	3	Yes	Toxicity resolves to \leq Grade 1 or baseline	Restart at same dose	Toxicity does not resolve to \leq Grade 1 or baseline by the time of next treatment dose. Permanent discontinuation should be considered for any severe or life-threatening event
	4	Yes	Discontinue treatment	Treatment may not be restarted	Yes.

Criteria to resume treatment:

Subsequent dosing with study therapy may resume once AEs resolve to Grade 1 or baseline.

Participants experiencing AEs not meeting criteria for permanent discontinuation as outlined in **Section 5.5** may resume treatment with study medication under the following criteria:

- Participants may resume treatment with study treatment when the drug-related AE(s) resolve to Grade \leq 1 or baseline value, with the following exceptions:
 - Participants may resume treatment in the presence of Grade 2 fatigue.

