8.4.3 DSMC Reporting by the Sponsor Investigator

Serious adverse events not constituting unanticipated problems are to be reported to the HICCC DSMC. Reporting should occur within 24 hours of knowledge of the SAE occurring at our institution or affiliate sites.

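### Toxicity boundary: the rule sentence only halts accrual, the worked example stops the trial, and neither says what happens to doses still due

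*Combined protocol and SAP*

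**What the plan says.** The rule stands under Continuous Toxicity Monitoring, after section 11.2.17. A dose-limiting toxicity is a treatment-related grade 3 or 4 event. Table 3 gives a boundary count b_n for each n, counted "out of n patients with full follow-up". The consequence of reaching it is stated as "The accrual will be halted if excessive numbers of dose-limiting toxicities are seen". The example under Table 3 takes 12 of the first 20 anti-IL-8 patients: if they "experience dose-limiting toxicities, the trial will be stopped for safety".

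Neither sentence mentions doses still due. The related provisions are these:

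- Section 7.1: "Day 15 dose will be given if still hospitalized". The day 29 dose is optional.
- Section 4.1: "Patients who are discharged prior to 2 weeks after the first treatment, will not receive additional doses of therapy".
- Section 7.6 lists reasons to end treatment. All concern the individual patient, and a boundary crossing is not among them.
- Section 7.9: "if toxicities occur, subsequent doses of BMS-986253 should follow the below guidelines". The guidelines deal with a patient's own toxicity.
- Section 8.4.3 sends serious adverse events that are not unanticipated problems to the DSMC: "Reporting should occur within 24 hours of knowledge of the SAE occurring at our institution or affiliate sites".
- Sections 12.3 and 12.4: the DSMC meets twice a month, and the Compliance Coordinator summarizes toxicities and stopping-rule status for it. The Stopping Rules paragraph lets the DSMC, the FDA or other regulators discontinue the study.

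**The concern.** One trigger carries two instructions. Halting accrual keeps new patients out; stopping the trial also reaches patients already on treatment. Staff who follow the rule sentence could give a due day 15 dose to a hospitalized patient with no toxicity of their own, although the group-level limit has been passed. Staff who follow the example would not. An accrual halt also achieves nothing if the crossing comes after the last anti-IL-8 patient has enrolled, and that can happen because the count waits for full follow-up.

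This is the plan's only numeric group-level toxicity rule, and the protocol justifies it by noting that anti-IL-8 has not been tested before in severe COVID-19. At stake is whether the action at a crossing is settled in advance or has to be worked out at that moment.

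**Working it through.** **1. Do both sentences describe the same event?** Table 3 gives a boundary of 12 for n = 19 to 21, so 12 of 20 is a true crossing. The exact 95% interval for 12/20 is (0.361, 0.809), matching the stated (0.36, 0.81). They do describe the same event.

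**2. Is the boundary itself right?** I used an exact binomial recursion over n = 1 to 92: after each patient the distribution of the toxicity count is updated with rate p, and any mass at or above b_n is removed as a first crossing. Two irregular column labels were read as 68–70 and 88–90.

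| True toxicity rate | Probability of crossing |
|---|---|
| 10% | 0.0001 |
| 20% | 0.0026 |
| 30% | 0.0496 |
| 40% | 0.510 |

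The plan states at most 0.05 at 30%, which is reproduced. The largest pointwise level is 0.0093 (n = 36), consistent with the stated 0.009 after rounding.

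**3. How many patients could have dose 2 pending?** The plan states no accrual period. Three values of D can be taken from it: 2.6 months (Table 4 shows an expected N of 138 at that month), 7 months (Table 4's final analysis) and 12 months (study duration in the synopsis). Assuming even accrual of the 92 and 30.44 days per month, the number between dose 1 and day 15 is 92 × 14 / D.

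Dose 2 needs the patient still in hospital. As a rough lower guide, take the plan's exponential medians of 2 and 5 days to improvement. The fraction unimproved at day 14 is 0.5^(14/2) = 0.0078 to 0.5^(14/5) = 0.144.

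| Accrual | D (days) | Between dose 1 and day 15 | Of these, unimproved at day 14 |
|---|---|---|---|
| 2.6 months | 79.1 | 16.3 | 0.13 to 2.3 |
| 7 months | 213.1 | 6.0 | 0.05 to 0.87 |
| 12 months | 365.25 | 3.5 | 0.03 to 0.51 |

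Improvement is not discharge: a patient moving from ventilation to supplemental oxygen has improved 2 points and is still hospitalized. The number with dose 2 truly pending therefore lies between the last two columns (deaths ignored). Optional day 29 doses are not counted.

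**4. How likely is a first crossing after the arm is full?** This depends on the follow-up window w, which the rule does not define. With w of 14 or 28 days (an assumption), the number countable when the arm fills is 92 × (D − w) / D. The probability is the recursion's first-crossing mass above that n.

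| Accrual | Countable (w = 14; 28) | At 30% | At 40% |
|---|---|---|---|
| 2.6 months | 75.7; 59.4 | 0.4% to 0.8% | 8% to 16% |
| 7 months | 86.0; 79.9 | 0.2% to 0.3% | 4% to 6% |
| 12 months | 88.5; 84.9 | 0.1% to 0.2% | 2% to 4% |

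At 20% every entry is below 0.0001. Section 8.2 defines study treatment follow-up as 100 days after the last dose. If that were the window, taken as 100 days per patient, about 49 (7 months) to 67 (12 months) would be countable, and the late-crossing probability would be 0.6% to 1.3% at 30% and 12% to 22% at 40%. Many of those crossings would come after dosing had ended, so they bear on the accrual-only wording and not on pending doses.

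**The case against.** The strongest reply is that the intent is plain. The paragraph speaks of a stopping boundary and a stopping rule, the example stops the trial, and Table 3 runs to n = 92, where an accrual halt would do little. Stopping a trial includes halting accrual, so the two sentences are not strictly incompatible. This stands as to intent: the gap lies in the sentence that states the rule.

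A second reply is that safeguards exist. Stopping-rule status is a named item in reports to the DSMC, which meets twice a month and may end the study. Serious events reach it within 24 hours of knowledge. Patients with their own grade 3 or 4 toxicity are mostly held under section 7.9. This also stands. What is missing is an action on dosing that takes effect at the crossing, before or without a DSMC meeting.

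A third is that the event is unlikely. In the monotherapy cancer study all related events were grade 1 or 2 (section 9.1.7), and at a 10% rate the crossing probability is 0.0001. COVID-19 patients may differ, but the practical risk is modest.

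A reader might go further and infer that the plan directs continued dosing after excess toxicity, that no one oversees a crossing, or that the boundary is miscalculated. The documents support none of these. The first isolates one clause from its own example, the second ignores sections 12.3 and 12.4, and the third fails on the reproduced 0.0496.

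**Conclusion.** The point holds as a modest safety clarification. The rule sentence and its example give different actions for the same trigger. Stopping is the evident intent, but no section fixes what happens to doses due at a crossing, and the literal rule does nothing once the anti-IL-8 arm is full.

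The size is uncertain. About 4 to 16 patients would be between dose 1 and day 15 at a time, with fewer still hospitalized at day 15. The upper end takes Table 4's N of 138 at month 2.6 at face value; the lower end assumes 12 months. A first crossing after the arm fills stays below 1% at a 30% toxicity rate and ranges from 2% to 16% at 40%, for an assumed 14- or 28-day window; a 100-day window gives higher values. All of this assumes even accrual. No boundary value, error rate or efficacy analysis is affected.

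**What to change.** Bring the rule sentence into line with the example and use the same words in both. For instance: if the boundary is reached, whether or not accrual is complete, accrual and further BMS-986253 dosing will stop, and may resume only if the DSMC so decides. Table 3 stays as it is.

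The cost is two sentences in a protocol amendment, using the existing DSMC, with no new staff, data or patients. The downside is that a few patients without toxicity may have a dose delayed or withheld while the DSMC decides.
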